Our study period will extend 11 years (January 2004 to December 2014), a period of rapid growth of HDHPs,²² capturing an unprecedented sample size of patients with bipolar disorder transitioning to HDHPs. The intervention cohorts will include individuals who transitioned to HDHPs between January 2005 (after a minimum one year baseline period in a traditional plan) and December 2013 (to allow one year of follow-up). We will follow all subjects for 1 year before and 1 year after the index month of switching (*Figure 3*). Matched controls will be drawn from employers who chose to remain in a traditional plan in the same calendar year, and our matching approach will ensure calendar month of switch is also balanced across the study groups. We will require continuous enrollment for the 24 month study period for both groups.

Figure 3. Study design of HDHP members and controls

* A subgroup of members are “forced switchers” whose employers mandate that they transition from a traditional to a high-deductible health plan

C.5 Study Population for Aims 1-3 [RQ-3; CI-1 to CI-4; HT-1 to HT-4]: Inclusion Criteria: We will include health plan members aged 12 to 64 years at the beginning of the baseline period. Consistent with prior research,⁸⁹⁻⁹¹ we will use medical claims data and a validated algorithm^{36,41,43-45,92,93} to identify members who had at least two ambulatory encounters or one hospital encounter with a diagnosis of bipolar disorder (ICD-9 diagnostic codes: bipolar-I: 296.0, 296.1, 296.4-296.7; bipolar-II: 296.89; and bipolar-other: 301.11 and 301.13^{43-45,89-91}). The first advisory panel committee meeting in October 2015 directly shaped our cohort definition stream of work; advisors agreed that bipolar inclusion criteria should include requiring at least 1 inpatient or 2 outpatient diagnoses, to better ensure that the diagnosis is valid and relevant to the planned analyses. Despite the tightening of our diagnostic criteria, our newest cohort totals remain on target with the estimates in our original power analysis. Eligibility for the study is predicated on the principal diagnosis of bipolar disorder (any diagnosis) not just diagnosis at the first position, as advised by our stakeholder panel. The study cohort was derived through applying the following inclusion rules, therefore defining individuals as eligible for our study:

[name]

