C.9 Analysis Plan for Aims 1-3 [IR-3; HT-1 to HT-4]: Overview: These analyses will determine how specific outcomes change after employer-mandated switching from traditional plans to HDHPs. To address methodological standard IR-3, we plan to use the most rigorous quasi-experimental retrospective longitudinal designs and analyses available for AIMS 1-3, namely interrupted time series with comparison series matched on multiple baseline covariates as well as the baseline trend of outcome measures. For Aim 4 we will use appropriate standard techniques for qualitative analyses of interview data (detailed below). We will first compare the characteristics of our matched cohorts (HSA-eligible and HSA-ineligible HDHP members, and traditional plan controls) using chi-square tests, t-tests and Poisson or quantile regression.¹²⁶ We will contrast sociodemographic characteristics, employer characteristics, and baseline health care utilization. Subsequent analyses will use time-series plots and rigorous analytical methods appropriate for each outcome, described below. Data collected on the same individuals in successive years are correlated (“repeated observations”). The extended general linear models—generalized estimating equations (GEE) and generalized linear mixed models (GLMM) for binary, count, or continuous measured outcomes—are appropriate methods for estimating parameters to adjust for these correlations within subjects.^{82,83} The term of interest in our GEE or GLMM models will be the interaction between *time* (pre versus post) and *cohort* (HDHP versus traditional plan). Statistical analyses in Aims 1-3 will first compare those transitioning to HDHPs with patients remaining in traditional plans; then contrast effects between HDHP members with full drug cost-sharing (HSA-eligible plans) and those transitioning to HDHPs without full drug cost-sharing (HSA-ineligible HDHPs). Each HDHP group will have as controls only those traditional plan members paired to a given HDHP member during the propensity score match. To examine possible selection effects due to applying our enrollment criteria and propensity matching approaches (see C.10), we will also compare our analytic population to members with bipolar disorder who were excluded from the sample.^[MD-4; CI-2]

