(Aim 1) Access to Appropriate Outpatient Care: We will assess changes before and after the index month in the *utilization and adherence* outcomes listed in C.7 for Aim 1 using patient-level *interrupted time series with comparison series*. The interrupted time series design includes multiple observations over time both before and after an intervention (i.e., the plan switch) and adjusts for most threats to internal validity (e.g., secular changes in prescribing, aging of the population) because it adjusts for baseline trends in study outcomes that are unrelated to the intervention.⁸⁰ Furthermore, our strategy of matching on the baseline outcome trend should generate highly robust causal estimates. We will use patient-level segmented linear regression models^{58,84} to statistically estimate patient-level changes in both level and trend in outcomes after the switch to HDHPs, while controlling for autocorrelation of the data and individual-level covariates. The segmented regression models include a constant term; an integer variable indicating *time* in months (t) from the start of the observation period to estimate baseline trend; a binary variable, *intervention*, indicating the period after the index month, to estimate change in level; and an interaction between *intervention* and *time*, to estimate change in trend. We will test the statistical significance of level or trend changes, adjusting for first-order autocorrelation between sequential monthly measurements using the empirical sandwich estimator in GEE.⁵⁸

For selected quality measures (i.e., likelihood of a quarterly outpatient mental health visit or receiving

guideline-recommended lab monitoring when using lithium, valproate, carbamazepine, and 2nd generation antipsychotics; C.7), our approach will be a pre-post with comparison group and difference-in-differences design. Logistic regression models will assess the independent effect of HDHPs on these outcomes, while controlling for patient-level covariates and secular utilization trends (by including index month).^{54,55,99}

(Aim 2) Adverse Patient Clinical Outcomes: To examine the impact of transitioning to HDHPs on changes in rates or risk of psychiatric/non-psychiatric ED visits and hospitalizations, we will use a pre-post with comparison group difference-in-differences design. We will control for patient-level covariates in the models. We will use GLMM to model the effect of HDHPs on annual hospitalization days.

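### As C.9 describes them, patient covariates and index month add no control for differential change in the balanced Aim 1 and 2 panels; covariate-by-period terms should be stated

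*Combined protocol and SAP*

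**What the plan says.** The C.9 overview defines the effect as a change: "The term of interest in our GEE or GLMM models will be the interaction between" time (pre versus post) and cohort (HDHP versus traditional plan). The models are then described by outcome.

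- **Aim 1 utilization and adherence:** "We will use patient-level segmented linear regression models" will estimate level and trend changes "while controlling for autocorrelation of the data and individual-level covariates". The listed terms are a constant, a month counter, a post-switch indicator and the product of the last two.
- **Aim 1 quality measures (quarterly visits, lab monitoring):** "Logistic regression models will assess the independent effect of HDHPs on these outcomes", "while controlling for patient-level covariates and secular utilization trends (by including index month").
- **Aim 2:** "We will control for patient-level covariates in the models", with no form given.

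C.4 fixes the panel: "We will follow all subjects for 1 year before and 1 year after the index month of switching", and "We will require continuous enrollment for the 24 month study period for both groups". The member-level covariates in C.8 are fixed or baseline characteristics, such as bipolar type, age, sex, SES and baseline expenditures.

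Matching is a separate layer. C.6 uses four employer propensity strata, then four contemporaneous controls per HDHP member within a caliper of 0.6 SD of the propensity score, and includes the baseline outcome in the match. C.4 adds that controls come from the same calendar year and that the month of switch is balanced.

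**The concern.** A before-after contrast removes anything constant within a person. A covariate that only raises or lowers all of a member's months is already gone from the contrast, so entering it again as a main effect adjusts for nothing that could still confound. What can confound is a covariate that predicts how much the outcome changes: sicker members drifting differently, for example, or a calendar period in which change was larger. Controlling for that requires the covariate, or the calendar period, to be crossed with pre/post.

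No such term is stated, yet C.9 credits the regression with covariate and secular-trend control. In the linear models, the adjusted estimate would equal the unadjusted one, and a reader would take their agreement as evidence of robustness. Any imbalance left by the match in a predictor of change would pass straight into the HDHP effect.

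**Working it through.** **1. The plan's own figure.** C.10 gives no figure for this point. Its nearest one is a detectable fall from 10% to 8% with 2160 versus 8640 members at 80% power. As a single-period, two-sided comparison of proportions it reproduces: 2117 HDHP members needed with continuity correction, 82.0% power at 2160 without it, and a minimum detectable decrease of 19.5%. It does not depend on the covariates.

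**2. Linear models: algebra.** Write Y(i,t) = a + b·g(i) + c·p(t) + d·g(i)·p(t) + θ·x(i) + error, where g is cohort, p is post and x is a baseline covariate. Every member supplies the same months, so the estimate of d is

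(mean post − mean pre, HDHP) − (mean post − mean pre, control).

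The term θ·x(i) appears equally in a member's pre and post means and cancels. The same holds for level and trend change under any working covariance common to all members. If instead the expected change in the absence of an effect is λ·x(i), the estimate is d + λ·(mean x in HDHP − mean x in controls), with or without θ·x(i) in the model. Only an x-by-post term removes the second part.

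**3. Linear models: numerical check.** Simulated balanced panel with an imbalanced covariate that predicts change (assumed data, simulated effect −0.030):

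| Quantity | No covariates | Main effects (covariates, index month) | Covariate × period |
|---|---|---|---|
| Difference-in-differences | −0.00533 (SE 0.00828) | −0.00533 (SE 0.00828) | −0.02896 (SE 0.00774) |
| Segmented level change | −0.01858 (SE 0.01583) | −0.01858 (SE 0.01583) | −0.04221 (SE 0.01551) |
| Level change, AR(1) weights at 0.3 | −0.02083 | −0.02083 | −0.04564 |

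The first two columns agree to eight or more decimals. In a separate GEE fit with an AR(1) working correlation, the two estimates were 0.006421 and 0.006416. A gap of that size is expected if the correlation is re-estimated in each fit.

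**4. Log-link counts.** The Poisson score equations force fitted totals to equal observed totals in the four cohort-by-period cells. A person-constant factor sums to the same amount before and after, so the ratio of rate ratios is unchanged. Check: 0.82979 in both fits. A random-effects model for hospitalization days was not run.

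**5. Balanced logistic models.** Here the coefficient does move. With covariate log-odds of 0.5 to 1.5 per SD, the smallest shift was 0.7940 to 0.7908 (0.4%) and the largest 0.8533 to 0.7991 (6.4%). Index month alone moved the odds ratio by at most 0.0004. This is non-collapsibility. Over 150 simulations at 2160 versus 8640, the mean coefficient went from −0.2321 (SE 0.1149) to −0.2532 (SE 0.1254), but the mean z was −2.018 versus −2.016, the largest difference in z was 0.023, and the rejection rate was 0.56 in both.

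With a true odds ratio of 1.00 and a covariate-by-period log-odds of 0.2 per SD:

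| Imbalance | No covariates | Main effect | Covariate × period |
|---|---|---|---|
| 0.1 SD | 1.020 | 1.023 | 1.007 |
| 0.5 SD | 1.071 | 1.088 | 1.009 |

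**6. Unbalanced denominators.** C.7 limits lab monitoring to users of specific drugs. If user status is set separately before and after, composition can shift. A simulation of that case with a true odds ratio of 1.00 gave 1.168 without the covariate and 0.982 with its main effect.

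**7. Illustration of size (all inputs assumed).** Take an SD of individual change in adherence of 20 points, λ = 2 points per SD and a residual standardized difference of 0.1 to 0.2. Bias = 0.1 × 2 to 0.2 × 2 = 0.2 to 0.4 points. SE = 20 × √(1/10,800 + 1/43,200) = 0.215 points, so a two-sided 5% test rejects a true null 15% to 46% of the time. For 1525 versus 6100 (the HSA group, 1:4), SE = 0.573 points and rejection is 6% to 11%. With λ = 1, rejection in the whole cohort is 8% to 15%.

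**The case against.** The main-effects reading is inferred. The segmented term list is visibly abbreviated: it omits cohort and every cohort interaction, although the overview makes time by cohort the term of interest. An unlisted covariate-by-period term is therefore not strictly excluded. This stands as a caution. However, C.9 does write out an interaction elsewhere (study group by period by SES, for disparities, if power permits), so the plan states such terms when it has them in mind.

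Secular trend is largely handled by design. Controls are contemporaneous and balanced on month of switch, so a common trend is differenced out and an index-period-by-post term should be nearly orthogonal to the effect. This stands too: for index month the fault is in what the sentence credits, and no bias is shown.

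Differential change is partly addressed by matching on covariates and on the baseline outcome and its trend, and by the stratified analyses. Relying on matching is legitimate, but C.9 claims regression control in addition. A 0.6 SD caliper and only four employer strata also leave room for residual imbalance.

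A reader might infer that the adjustment does nothing anywhere. The documents do not support that. The logistic odds ratio shifts, user-only denominators may be unbalanced so that main effects help, and the covariates also act through the match.

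**Conclusion.** The point holds in a limited form. If the covariates and index month enter as person-constant main effects, the regression adjustment adds no control for covariates that predict differential change in the balanced panels. That is exact for the linear segmented models (given a common working covariance) and for log-link counts. In balanced logistic models the odds ratio moves while the test is essentially the same. Index month as a main effect does not control secular trend. Lab monitoring among drug users is a possible exception, depending on how user status is defined.

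It would be tempting to conclude that the HDHP estimates are biased, or that false-positive rates will reach 15% to 46%. Neither follows. The documents give no residual imbalance, no slope on change and no SD of change, so step 7 is illustration only. Even there, 0.2 to 0.4 points is about 7% to 13% of the 3-point adherence change (49% to 46%) used in C.10. The change is still worth making, because the stated adjustment cannot remove whatever imbalance the match leaves, and a nearly free addition could.

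**What to change.** In C.9:

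- Keep the main effects and add centred baseline covariates (ACG score, age, sex, bipolar type, SES, baseline expenditures, coverage tier) crossed with the post period. In the segmented models, cross them with level change and trend change.
- State that the effect of interest remains cohort by period, or cohort by level and trend change, and list those cohort terms.
- Replace the claim that index month controls secular trends with an index-calendar-period by pre/post term, or say that secular trend is handled by the contemporaneous matched controls. This part is expected to change the estimate little.
- For lab monitoring, say whether drug-user status is fixed at baseline or set per period.

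The cost is some wording, a few more model terms and slightly more analysis work on data already being built. The loss of degrees of freedom is negligible at these sample sizes, and centring keeps the effect interpretable.

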C.10 Sample Size Estimates and Power Calculations [HT-1 to HT-4]: Using 10 years of data (2003-2012), we found 42 million unique adolescents and adults aged 12-64, approximately 450,000 of whom (~1%) had at least one bipolar disorder diagnosis. This is consistent with our expectation of a lower disease prevalence among commercially-insured adults compared with the 3% prevalence estimated by epidemiological surveys,³ because individuals with bipolar disorder less commonly have private insurance.¹³¹ A total of 109,012 of the 450,000 with a bipolar diagnosis met our inclusion criteria of 2 years continuous enrollment, with the first year in a traditional plan, the second in a traditional or HDHP, and no choice from the employer at any point regarding plan type. Projecting to 2014, our sample will include over 10,800 HDHP members (1525 HSA and 9275 non-HSA) and 43,200 matched traditional plan controls with bipolar illness (1:4 matching). Our smallest HDHP subgroups examined for primary outcomes will include 1525 HSA members (smallest medication adherence cohort) and 2160 non-white members (smallest emergency department and hospitalization outcome cohort).

For interrupted time series analyses of medication adherence, based on assumptions including 12 months of follow-up, autocorrelation of less than 0.3, and 0.05 type I error,¹³² we will have greater than 90% power to detect a 6% relative decrease in adherence in our smallest medication outcome subgroup (HSA-HDHP members). For example, we could detect an adherence rate change from 49% (as seen in previous literature¹³³) to 46% with a standard deviation of 1.5%. This is a *smaller* change in adherence than has been observed previously in HDHP-HSA studies.⁵⁷

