We will use generalized estimating equations to model difference-in-differences analyses of our least frequent outcomes, including emergency department visits and hospitalizations. Based on the smallest subgroup of 2160 non-white HDHP members and their 8640 matched traditional plan controls, a baseline psychiatric hospitalization rate of 10% per year,⁸⁹ (the lowest rate among our measures), 0.05 type I error, 80% power, and a conservative repeated observations correlation assumption of 1, we will be able to detect a 20% relative decrease (e.g., from 10% to 8%). This is smaller than the 27% hospitalization decline we detected in a previous HDHP study.⁵⁴ We will have more power to detect changes for all other outcomes. The power estimates were calculated using PASS software.¹³⁴

C.11 Study Population and Methods for Aim 4 [RQ-3; PC-2]: Ours will be the first qualitative study to explore views of patients with bipolar illness regarding insurance-related barriers to care and experiences with commercial insurance benefits. Qualitative results will complement and inform our quantitative claims-based analyses in Aims 1-3. For Aim 4, DBSA will assist in recruiting **individuals living with bipolar disorder or close family members** to participate in semi-structured telephone interviews. The opportunity to volunteer for participation in interviews will be presented in local DBSA chapter in the form of a flyer for attendees. These flyers will be distributed by DBSA to chapter leadership by means of US mail, email, and routine in-person outreach visits by DBSA officials to chapter meetings. Interested individuals who see the flyer will telephone our co-investigator [name] at DBSA in Chicago. [name] will conduct an initial screening for eligibility, focused on insurance coverage type, English competence, and achieving a rough US geographic balance. [name] will transmit contact details of individual interested in participating to the DPM/HPHCI team. We anticipate identifying ~100 candidate respondents at DBSA, to allow for drop-out due to additional screening, scheduling conflicts, non-consent, etc. In order to achieve full saturation of themes, we anticipate needing 40 completed interviews, as described below. We will schedule more interviews (~60 in total) in order to pilot test our instrument and to account for partial or non-informative interviews.

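### C.10's inputs for adherence power give about 57–68% in the planned segmented model on a single monthly series, not the stated 90% or more

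*Combined protocol and SAP*

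**What the plan says.** Section C.10 (Sample Size Estimates and Power Calculations) names the cohort: "Our smallest HDHP subgroups examined for primary outcomes will include 1525 HSA members", the smallest group for medication adherence. For that group it claims "greater than 90% power to detect a 6% relative decrease in adherence in our smallest medication outcome subgroup", "based on assumptions including 12 months of follow-up, autocorrelation of less than 0.3, and 0.05 type I error". The worked example is a fall from 49% "to 46% with a standard deviation of 1.5" percent. C.10 then describes this as a smaller "change in adherence than has been observed previously in HDHP-HSA studies".

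Section C.9 (Aim 1) sets the analysis. It is a patient-level segmented linear regression with a constant, a monthly baseline trend, a level change and a trend change. It includes a comparison series and is fitted by GEE with a sandwich variance. Section C.4 gives one year before and one year after the switch, so there are 12+12 monthly points.

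For hospitalization, the next paragraph of C.10 gives the group sizes, "2160 non-white HDHP members and their 8640 matched traditional plan controls", and "a conservative repeated observations correlation assumption of 1". The adherence paragraph states neither a control number nor a within-patient correlation.

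**The concern.** A segmented model that estimates its own baseline trend has a much less precise level change than a plain before-and-after comparison of means. With 24 monthly points and a 3-point change equal to two SDs, power above 90% looked too high for the C.9 model.

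C.10 offers this figure for the HSA-eligible cohort, where drugs fall under the deductible. C.10 uses it to say that the detectable change is smaller than earlier studies observed. The limitations section (the second section numbered C.11) refers to C.10 when it adds that 12 months should be enough. If the figure is not supported, a null adherence result in HSA members could be read as more reassuring than C.10 justifies.

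**Working it through.** **Inputs.** Change 49 − 46 = 3 points, SD 1.5 points, alpha 0.05 and autocorrelation (rho) below 0.3, all from C.10. There are 12+12 months (C.4) and the model terms come from C.9. My assumptions are a two-sided test, since C.10 does not state sidedness, and 0 as the lower end of rho. The relative change reproduces: 3/49 = 6.1%.

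**What 1.5% can mean.** The binomial standard error of a 49% rate in 1525 people is √(0.49 × 0.51/1525) = 1.28 points, so 1.5 points is a sensible size for month-to-month scatter in an aggregate rate. The other readings do no better:
- As the standard error of the change: 3/1.5 = 2.0, power Φ(2.0 − 1.96) = 52%.
- As a patient-level SD: the detectable change would be about 0.10 to 0.12 points, so it cannot underlie a 3-point limit.

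**Single series, C.9 model.** With columns 1, t, post and post × (t − 12) for t = 1 to 24, and AR(1) correlation matrix R:

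SE(level change) = 1.5 × √[(X′R⁻¹X)⁻¹]₃₃, where the root is 0.8208 at rho 0 and 0.9391 at rho 0.3.

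Power = Φ(3/SE − 1.960) two-sided, or Φ(3/SE − 1.645) one-sided.

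| rho | SE | 3/SE | two-sided | one-sided |
|---|---|---|---|---|
| 0 | 1.231 | 2.437 | 68% | 79% |
| 0.3 | 1.409 | 2.130 | 57% | 69% |

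Dropping only the trend-change term leaves 69% to 57%. Positive autocorrelation within the stated range lowers power. A rho of about −0.35 would be needed to reach 90%.

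**Detectable change at 90% power.** (1.960 + 1.2816) × SE = 3.2415 × SE, which is 3.99 points at rho 0 and 4.57 at rho 0.3. Relative to 49, that is 8.1% and 9.3%. For 3 points to be detectable, the monthly SD would have to be 3/(3.2415 × 0.8208) = 1.13 or 3/(3.2415 × 0.9391) = 0.99, against the printed 1.5.

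**Where more than 90% does appear.**
- *Printed inputs, no trend terms, pre and post means compared.* At rho 0 the SE is 1.5 × √(2/12) = 0.612 and power is 99.8%. At rho 0.3 the SE is 0.782 and power is 97%. C.9 does not plan this model.
- *A comparison series added.* The SE is multiplied by √(1 + k² − 2ck), where k is the control SD divided by 1.5 and c is the correlation between the two series. With k = 1 and c = 0, power falls to 41–32%. With k = 0.5 and c = 0 it is 59–48%. With k = 0.5 and c = 0.75 it rises to 93–85%. C.10 gives neither k nor c.
- *Stable between-patient variation inside the 1.5%.* In a closed cohort this part cancels from the level change. The share needed for 90% power is 1 − (1.128/1.5)² = 43% at rho 0 and 1 − (0.986/1.5)² = 57% at rho 0.3. C.10 gives no such share.

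**Planned patient-level model.** With 1525 members, 90% power needs a month-to-month patient SD, after removing stable differences between patients, of at most 1.128 × √1525 = 44.0 points (rho 0) to 0.986 × √1525 = 38.5 points (rho 0.3). With 1:4 independent controls of equal SD, dividing by √1.25 gives 39.4 to 34.4 points. If the total SD were 50 points (assumed), a stable share of 38–53% would meet the limits with controls. These limits ignore any correlation among employees of one employer. The documents do not say on which side of them the data lie.

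**The case against.** The strongest reply is that the single-series figure is not a verdict on the planned design. C.9 plans a patient-level model with a comparison series, and C.4 requires continuous enrollment throughout, so stable patient differences drop out of the level change. C.10 presents its assumptions as a partial list and cites a simulation-based method that may define the SD and the tested effect. Nothing printed is miscalculated, and the cohort is all eligible members, so the power figure sets neither sample nor follow-up.

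Much of this stands. A reader might infer that the HSA adherence analysis is underpowered. The documents do not support that: many plausible patient-level SDs and correlations give more than 90%. A reader might also infer that any version keeping the baseline trend falls short. That is too broad, because a highly correlated comparison series or a large stable share can reach 90%. Both routes, however, need inputs that C.10 does not print. The printed example therefore still fails to support its own claim.

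One could also make something of the cited simulation method beside the statement "The power estimates were calculated using PASS software". That sentence closes the hospitalization paragraph and may refer only to it. It adds nothing on its own.

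**Conclusion.** The concern holds as a mismatch between a stated power and its printed inputs. Taking 1.5% as the residual SD of the monthly rate, the C.9 segmented model on a single 12+12 month series gives 57–68% two-sided power (69–79% one-sided) for the 3-point change. At 90% two-sided power it detects 4.0–4.6 points. This rests on that reading of the SD, on AR(1) errors with known rho between 0 and 0.3, and on no contribution from controls. The power of the planned patient-level controlled model cannot be determined from C.10.

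The choice of 12 months is not undermined. The limitations section's main reason is differential dropout, which this does not touch. Only its added remark that 12 months is sufficient leans on C.10.

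**What to change.** Rerun the adherence power for the C.9 patient-level segmented model with its 1:4 controls and 12+12 months. Take the patient-level SD and within-patient correlation from baseline-year months in the claims already held (A.7 reports 9 of the 11 years in hand). Name the tested coefficient (level change, trend change or average post-switch effect) and the sidedness, and state what the SD refers to.

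Replace the C.10 power sentence with either the resulting power for 3 points or the change detectable with 90% power. Keep the comparison with earlier HDHP-HSA studies, and the remark that 12 months is sufficient, only if they still hold. The figures worked out here are conditional checks and should not be printed in their place.

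The cost is one rerun and one reworded paragraph. No new data are needed and cohort and follow-up do not change. The stated figure may become less favourable.
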